12. DATA HANDLING AND RECORD KEEPING

12.1. CRFs and Source Documentation

All data obtained during the study should be entered in the EDC system promptly. All source documents from which EDC entries are derived should be placed in the patient's medical records. Measurements for which source documents are usually available include laboratory assessments, ECG recordings, CT scans, MRI, and X-rays. EDC entries may be checked against source documents at the study site or remotely by the Sponsor or Sponsor's designee site monitor. After review by the site monitor, completed EDC entries will be uploaded and forwarded to the Sponsor (or designee). Instances of missing or uninterpretable data will be discussed with the Investigator for resolution.

The specific procedures to be used for data entry and query resolution using the EDC system will be provided to study sites in a training manual. In addition, site personnel will receive training on the EDC system.

12.1.1. Data Collection

The Investigators (and appropriately authorized staff) will be given access to an online web-based EDC system that is compliant with the ICH guidelines for Good Clinical Practice (ICH E6). This system is specifically designed for the collection of clinical data in electronic format. Access and rights to the EDC system will be carefully controlled and configured according to everyone's role throughout the study. In general, only the Investigator and authorized staff will be able to enter data and make corrections in the eCRFs.

The eCRF should be completed for each patient included in the study and reflect the latest observations on the patient. Therefore, the eCRFs are to be completed as soon as possible during or immediately after the patient's visit or assessment. The Investigator must verify that all data entries in the eCRF are accurate and correct.

Computerized data--check programs and manual checks will identify any clinical data discrepancies for resolution. Corresponding queries will be loaded into the system, and the site will be informed about new issues to be resolved online. All discrepancies will be solved online directly by the Investigator or authorized staff. Offline edit checks will be done to examine relationships over time and across panels to facilitate quality data.

After completion, the Investigator will be required to electronically sign off the clinical data.

Data about all study drug dispensed or administered to the patient and any dosage changes will be tracked in the eCRF.

12.2. Access to Source Data

Patients are informed about who may have access to their medical records and study data. During the study, a monitor will make site visits or conduct remote monitoring to review protocol compliance, compare EDC entries and individual patient's medical records, and ensure that the study is being conducted according to pertinent regulatory requirements. EDC entries will be verified with source documentation. The review of medical records will be performed in a manner to ensure that patient confidentiality is maintained. Appropriate access controls will be in place to ensure that access to confidential research information is restricted to those who need access.

Checking of EDC entries for completeness and clarity and cross-checking with source documents will be required to monitor the progress of the study. Moreover, Regulatory Authorities of certain countries, IRBs, IECs, and/or the Sponsor's Clinical Quality Assurance Group may wish to carry out such source data checks and/or on-site audit inspections. Direct access to source data will be required for these inspections and audits; they will be carried out giving due consideration to data protection and medical confidentiality. The Investigator assures the Sponsor (or designee) the necessary access at all times.

12.3. Data Processing

All data will be entered by site personnel into the EDC system. The data-review and data-handling document, to be developed during the initiation phase of the study, will include specifications for consistency and plausibility checks on data and will also include data-handling rules for obvious data errors. Query/correction sheets for unresolved queries will be sent to the

study monitors for resolution with the Investigator. The database will be updated based on signed corrections.

Concomitant medications will be coded using the WHO Drug Global dictionary, which employs the Anatomical Therapeutic Chemical classification system. Medical history, current medical conditions, and AEs will be coded using MedDRA terminology. The versions of the coding dictionaries will be provided in the clinical study report. When personal data is transferred electronically, data will be encrypted during transfer.

12.4. Archiving Study Records

The Investigator shall retain study drug disposition records and all source documentation (such as original ECG tracings and laboratory reports, in subject or office subject records) for the maximum period required by the country and institution where the study will be conducted or for the period specified by Rain, whichever is longer. The investigator must contact Rain prior to destroying any records associated with the study. If the investigator withdraws from the study (due to relocation, retirement, etc.), the records shall be transferred to a mutually agreed upon designee, such as another investigator or IRB/IEC. Notice of such transfer will be provided in writing to Rain.

Rain Therapeutics Inc. will maintain archive copies of all records for a period of no less than 25 years.

13. PUBLICATION POLICY

By signing the study protocol, the Investigator agrees with the use of results of the study for the purposes of national and international registration, publication, and information for medical and pharmaceutical professionals. If necessary, Regulatory Authorities will be notified of the Investigator's name, address, qualifications, and extent of involvement.

An Investigator shall not publish any data (poster, abstract, paper, etc.) without discussion with and approval by the Sponsor.

PFS	Progression-Free Survival
PK	Pharmacokinetics
PR	Partial Response
PT	Preferred Term
QoL	Quality of Life
RECIST	Response Evaluation Criteria in Solid Tumors
SAE	Serious Adverse Event
SAP	Statistical Analysis Plan
SD	Stable Disease
SOC	System Organ Class
TEAE	Treatment-Emergent Adverse Event

TP53	Tumor Protein 53
TTP	Time to Progression
WHODrug	World Health Organization Drug Reference List

1. INTRODUCTION

This statistical analysis plan (SAP) outlines the statistical methods to be implemented within the scope of Protocol RAIN-3202 entitled “A Phase 2 Basket Study of Milademetan in Advanced/Metastatic Solid Tumors”. The purpose of the SAP is to ensure the credibility of the study findings by pre-specifying the statistical approaches to the analysis of study data prior to data base lock. Results of the proposed analyses in this SAP will become the basis of the clinical study report (CSR) for this protocol.

2. STUDY OBJECTIVES

2.1 Primary Objective

[figure not shown]
The primary objective is to determine the objective response rate (ORR) of treatment with milademetan in patients with advanced/metastatic solid tumors with murine double minute 2 (*MDM2*) gene amplification.

2.2 Secondary Objectives

The secondary objectives are:

- To assess treatment with milademetan for the following efficacy parameters:
 - Duration of response (DOR)
 - Progression-free survival (PFS)
 - Growth modulation index (GMI)
 - Disease control rate (DCR)
 - Overall survival (OS)
- To assess the safety profile of milademetan
- To evaluate patient-reported health-related quality of life with the European Organisation for Research and Treatment of Cancer Quality-of-Life Questionnaire, Core 30 (QLQ-C30)

2.3 Exploratory Objectives

3. STUDY DESIGN OVERVIEW

3.1 Overall Design

[figure not shown]
This is a Phase 2, multicenter, single-arm, open-label basket study designed to evaluate the safety and efficacy of milademetan in patients with advanced or metastatic solid tumors refractory or intolerant to standard-of-care therapy that exhibit wild-type (WT) tumor protein 53 (*TP53*) gene and *MDM2* copy number (CN) ≥ 8 using prespecified biomarker criteria.

Approximately 65 patients will be enrolled to receive milademetan.

Patients will receive the study drug until reaching disease progression (per Response Evaluation Criteria in Solid Tumors [RECIST] version [v]1.1), as determined by the Investigator; experiencing unmanageable toxicity; or until other treatment discontinuation criteria are met. Patients may be treated beyond tumor progression if they are experiencing clinical benefit based on the assessment of the Investigator in discussion with the Medical Monitor.

All patients will be followed for documentation of disease progression and survival information (i.e., date and cause of death). Long-term follow-up will continue every 8 weeks (± 7 days) until the endpoint of death, the patient is lost to follow-up, or for 24 months following the final dose of the study drug, whichever comes first.

3.2 Sample Size Considerations

4. STUDY ENDPOINTS AND COVARIATES

4.1 Primary Endpoint

The primary efficacy endpoint is ORR. The ORR is defined as the percentage of patients who have achieved a confirmed CR or PR. Tumor response will be assessed in accordance with RECIST v1.1.

4.2 Secondary Endpoints

[figure not shown]
Secondary efficacy endpoints include:

- The DOR, defined as the time from the date of first response to the date of disease progression or death for patients with an objective response
- The PFS, defined as the time from the date of first dose to the earliest date of the first objective documentation of radiographic disease progression or death due to any cause
- The GMI will be determined using the ratio of time to progression (TTP) with n^{th} line of therapy (TTP_n ; here defined as milademetan) to the most recent prior line of therapy (TTP_{n-1})
- The DCR, defined as the percentage of patients who have achieved confirmed CR, PR, or stable disease (SD) for ≥ 16 weeks
- Overall survival, as measured from the date of the first dose of the study drug to the date of death due to any cause

Health-related quality-of-life endpoints include the QLQ-C30.

Safety endpoints include the incidence of TEAEs (including SAEs, TEAEs leading to dose reductions and TEAEs leading to discontinuation of study drug); changes in clinical laboratory parameters (hematology, serum or plasma chemistry), deaths, vital signs, and ECG parameters (especially QT intervals); physical examination results; and use of concomitant medications.

4.3 Exploratory Endpoints

5. ANALYSIS POPULATIONS

5.1 Full Analysis Population

[REDACTED]

5.2 Centrally Confirmed Population

[REDACTED]

5.3 Pharmacokinetics (PK) Population

The pharmacokinetics population consists of all patients who have evaluable PK data. Exploratory pharmacokinetics analyses will be performed using the PK population.

6. STATISTICAL METHODS OF ANALYSIS

6.1 General Principles and Reporting Conventions

In general, efficacy and safety analysis in this study will be summarized across all tumor types. Analysis may be performed for specific tumor types when appropriate.

[REDACTED]

If departures from these general conventions are present in the specific evaluations section of this SAP, then those conventions will take precedence over these general conventions.

6.2 Subject Accountability

6.2.1 Disposition of Patients

The number and percentage of patients who were enrolled and treated with study drug will be tabulated. End of treatment and end of study will be summarized by reasons.

6.3 Demographic and Baseline Characteristics

Demographic data, medical history, concomitant disease, and concomitant medication will be summarized by means of descriptive statistics or frequency tables for the FAP.

6.3.1 Demographic Characteristics

The following demographic variables will be summarized:

- age (years)
- age group (<65, \geq 65 years)
- sex
- race (Asian, American Indian or Alaska Native, Black or African American, Native Hawaiian or Other Pacific Islander, White, Other)
- ethnicity (Hispanic or Latino, Not Hispanic or Latino)
- height (cm)
- weight (kg)
- body mass index (BMI) calculated as: $BMI \text{ (kg/m}^2\text{)} = \text{Weight (kg)}/(\text{Height(cm)} * 0.01)^2$

6.3.2 Baseline Disease Characteristics

The following baseline disease characteristics will be summarized:

- ECOG
- Number of prior lines of therapy
- Tumor type
- Stage at initial diagnosis
- Stage at study entry
- TNM stage
- MDM2 copy number (central and local)
- Time from initial diagnosis
- Time from metastatic diagnosis

- Tumor status
- Brain metastases (Present/Absent)

6.3.3 Prior Cancer Therapy

Prior radiation, cancer related surgery, cancer therapy will be summarized with indication. Number of prior lines of therapy for metastatic disease, best response of each line of therapy will be summarized.

6.3.4 Medical History

Medical history data will be summarized in frequency table. Medical history data including chronic conditions, relevant surgical procedures, symptoms, any medical conditions that require medication and cancer history will be collected at screening, within 14 days before Cycle 1/ Day1 in accordance with the Schedule of Procedures included in the protocol.

6.3.5 Prior and Concomitant Medications

Concomitant medications will be defined as medications documented on the Concomitant Medications CRF. Concomitant medications will be coded using the World Health Organization (WHODrug) dictionary B3 Global March 2021 and summarized in a frequency table.

6.4 Efficacy Analyses

The efficacy analysis of the study will be performed in the CCP. The analysis of ORR and other RECIST endpoints will be according to the investigator's tumor assessments.

[figure not shown]

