4. STUDY DESIGN

4.1. Study Design Overview

This is a Phase 2, multicenter, single-arm, open-label basket study designed to evaluate the safety and efficacy of milademetan in patients with advanced or metastatic solid tumors refractory or intolerant to standard-of-care therapy that exhibit WT *TP53* and *MDM2* CN ≥ 8 using prespecified biomarker criteria. Local lab results for determination of *TP53* mutation status

and *MDM2* amplification may be used for eligibility; verification of *MDM2* CN should be performed using a central laboratory as outlined under Section 5.1 Inclusion Criteria.

Approximately 65 patients will be enrolled to receive milademetan.

Patients will receive the study drug until reaching unequivocal disease progression (per RECIST v1.1), as determined by the Investigator; experiencing unmanageable toxicity; or until other treatment discontinuation criteria are met. Patients may be treated beyond tumor progression if patients are experiencing clinical benefit based on the assessment of the Investigator in discussion with the Sponsor's Medical Monitor.

All patients will be followed for documentation of disease progression and survival information (i.e., date and cause of death). Long-term follow-up (LTFU) will continue every 12 weeks (\pm 7 days) until the endpoint of death, the patient is lost to follow-up, or for 24 months after the first dose of the study drug for the last patient, whichever comes first.

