5. SELECTION AND WITHDRAWAL OF PATIENTS

5.1. Inclusion Criteria

Each patient must meet all of the following criteria to be enrolled in the study:

[figure not shown]
1. Is \geq 18 years of age at the time of signing informed consent
2. Has signed and dated an informed consent form prior to the start of any study-specific qualification procedures
3. Has histologically and/or cytologically confirmed diagnosis of a cancer that is a locally advanced or metastatic solid tumor
4. Has measurable tumor lesion(s) in accordance with RECIST v1.1
5. Must have received all standard therapy appropriate for their tumor type and stage of disease or, in the opinion of the Investigator, would be unlikely to tolerate or derive clinically meaningful benefit from appropriate standard-of-care therapy

6. Has resolution of any clinically relevant toxic effects of prior chemotherapy, surgery, radiotherapy, or hormonal therapy

[figure not shown]

7. Presence of WT *TP53* and *MDM2* gene amplification by tumor tissue/blood testing, defined as:
 - a. ≥ 8 copies in tumor tissue by central laboratory or
 - b. ≥ 8 copies or 4-fold increase in tumor tissue or blood by local testing

8. Has an ECOG performance status of 0 or 1
9. Has adequate bone marrow function, defined as:
 - a. Platelet count $\geq 100 \times 10^9/L$
 - b. Hemoglobin $\geq 9.0 \text{ g/dL}$
 - c. Absolute neutrophil count $\geq 1.5 \times 10^9/L$
10. Has adequate renal function, defined as creatinine clearance $\geq 30 \text{ mL/min}$, as calculated using the modified Cockcroft-Gault equation (or equivalent glomerular filtration rate calculated using the Chronic Kidney Disease Epidemiology Collaboration formula)
11. Has adequate hepatic function, defined as:

- a. Alanine aminotransferase and aspartate aminotransferase $\leq 3 \times$ the ULN if no liver metastases are present or $\leq 5 \times$ ULN if liver metastases are present
- b. Total bilirubin $\leq 1.5 \times$ ULN or $\leq 3 \times$ ULN in the presence of liver metastases. Patients with Gilbert's disease who have serum bilirubin levels of $> 3 \times$ ULN may be enrolled
12. Is willing and able to comply with the protocol requirements
13. If requiring anticoagulation medication, should be on a stable regimen, defined as being on the same dose for at least 4 weeks

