6. TREATMENT OF PATIENTS

6.1. Patient Enrollment

Selected patients may require central verification of *TP53* mutation status and /or *MDM2* amplification which can be performed under prescreening consent as outlined in the inclusion section.

Prior to any study-related assessments, all potential patients will provide written informed consent. After written informed consent has been obtained and eligibility has been confirmed, the study site will obtain the patient's identification number from the Interactive Response Technology System. Once a patient identification number has been assigned, it will be used to identify the patient throughout the study, and it cannot be reassigned to another patient.

Investigational sites will provide the Sponsor's Medical Monitor with a completed Eligibility Checklist for Sponsor review. Patients who meet the eligibility criteria may be enrolled. Patients will be considered enrolled upon their first dose of the study drug.

Patients who cannot complete the procedures within the Screening window or are not initially eligible may be rescreened. In this situation, a new patient identification number will be assigned. For rescreening within the original Screening window, certain Screening procedures may not need to be repeated. Reconsent is required for rescreening outside the original Screening window.

An Investigational Drug Accountability Log must be used for drug accountability. For additional details on investigational study drug management, please refer to the Pharmacy Manual. Patients will be provided with a patient diary to record study drug administration and compliance.

[figure not shown]

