6.8. Screening Period/Baseline Assessments

Patients may be screened at any time during the 21 days prior to the first dose of the study drug. Unless otherwise specified, Screening/baseline assessments may be done any time after consent and prior to the first dose of the study drug. Physical examination, ECOG, and clinical laboratory assessments on Cycle 1 Day 1 can be performed within 72 hours before the first dose of study drug. Patients who are determined not to meet eligibility criteria at any time prior to the first dose of the study drug will not be enrolled. The following will be assessed or measured at Screening/baseline:

- Informed consent

- Eligibility (including tumor assessment)
- Medical/disease history
- Smoking history: Smoking history should be documented on the eCRF page as “never,” “former” (with quit date), or “current” (document pack years)
- Demographics
- Physical examination focused on major organ systems that are clinically relevant as determined by the Investigator and including symptom directed findings and vital signs (taken 5 minutes after sitting), including height and weight
- ECOG Performance Status Scale
- ECG (12-lead) in triplicate
- Blood samples for laboratory assessments (see [Table 1](#)); ensure a serum pregnancy test is conducted for WOCBP
- Patient-reported outcomes: QLQ-C30
- Tissue as newly obtained biopsy or archived tissue \leq 5 years old for central diagnostic laboratory verification of WT *TP53* and *MDM2* CN. Tissue may be submitted as either:
 - FFPE block, or
 - at least 15 unstained, unbaked, positively charged slides with \geq 20% tumor tissue in 5-micron sections per slide as confirmed by a local pathologist

Note: Patients who have central testing of *TP53* and *MDM2* gene status performed under prescreening consent can forego this tissue submission requirement.

- In patients who provide consent to the optional procedure:
 - Tumor biopsy consisting of sufficient tissue to generate at least 15 slides of adequate quality
- Prior and concomitant medications:
 - Record all concomitant medication use after 21 days prior to Cycle 1 Day 1
 - Special attention should be accorded to medications that are known to cause prolongation of QTc or deplete potassium
- Baseline radiographic tumor assessment per RECIST v1.1:

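### Does running the efficacy analysis in the Centrally Confirmed Population leave treated patients out of the account?

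*SAP*

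**What the plan says.** SAP 6.4 is short in the public version: "The efficacy analysis of the study will be performed in the CCP". The protocol's abbreviation list expands CCP as Centrally Confirmed Population. SAP 6.3 summarises demographic and baseline data for the FAP, and SAP 6.5.1 does the same for safety. SAP 6.1 adds that where a specific section departs from its general conventions, "then those conventions will take precedence over these general conventions".

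Protocol 5.1, criterion 7, offers two routes joined by *or*. Route 7a is a central tissue result of at least 8 copies. Route 7b is at least 8 "copies or 4-fold increase in tumor tissue or blood by local testing". Protocol 6.1 fixes the moment of entry: "Patients will be considered enrolled upon their first dose of the study drug".

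Three places speak to central testing:

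- Protocol 4.1 lets local results be used for eligibility and says that verification of MDM2 "CN should be performed using a central laboratory as outlined under Section 5.1 Inclusion Criteria".
- Protocol 6.1 says "Selected patients may require central verification of" TP53 status and/or MDM2 amplification, which can take place under prescreening consent.
- Protocol 6.8 lists new or archived tissue for central verification among the Screening items. Its only stated exemption is for patients whose central testing was "performed under prescreening consent can forego this tissue submission requirement".

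The primary objective in SAP 2.1 is the ORR "in patients with advanced/metastatic solid tumors with murine double minute 2" gene amplification.

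**The concern.** In a single-arm trial the primary result is one proportion, so its denominator matters. A patient can meet 7b on a blood result or a 4-fold increase, be dosed, and later lack a confirming central tissue result. That patient would count in the baseline and safety tables but, judging by the population's name, not in the ORR. The three statements on central testing also differ in strength, so it is unclear at first reading how many patients this could affect.

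If the group were large and responded differently, the ORR would depend on the choice of set. The baseline table would also describe a different group from the one behind the ORR. The readable text names no FAP efficacy analysis and no count of FAP patients outside the CCP, and the planned table list has one ORR title with no population attached. It is natural to ask for both items.

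**Working it through.** **1. Does the CCP suit the question?** The objective concerns tumours with MDM2 amplification. A set built on central confirmation, if the name means what it says, targets that group directly. The choice is consistent with the objective.

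**2. How many patients could fall outside?** Read together, the three testing statements point to central testing for essentially every patient. Protocol 4.1 expects central verification. Protocol 6.8 asks for the tissue at Screening and excuses only those already tested centrally. The sentence in protocol 6.1 continues with the prescreening consent route, so it can be read as describing that route and not as making verification optional. None of this guarantees a confirming result before the first dose, so the group need not be empty.

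**3. Is any of it already tracked?** SAP 6.3.2 summarises both central and local MDM2 copy number, and SAP 6.3 places baseline summaries in the FAP. A biomarker summary table is also planned in SAP 8. These bear in part on who lacks a central value or falls below the threshold. They do not give response outside the CCP.

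**4. Where would the rest stand?** It would stand in the population definitions (SAP 5.1, 5.2), the general conventions (SAP 6.1), any text following SAP 6.4 and 6.4.1, SAP 7, the synopsis statistical methods, and protocol section 9. The protocol's table of contents lists 9.3.3 for analysis sets and 9.7.1 and 9.7.2 for the primary and secondary efficacy analyses. All of these are blacked out, partly blacked out or not shown. SAP 6.4 does not say that efficacy is analysed in the CCP alone. The precedence rule in SAP 6.1 settles conflicts between sections and does not bar an additional FAP analysis.

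**5. How large could the effect be?** The plan's only usable figure is about 65 enrolled, which means treated, since enrolment is the first dose. The public text gives no sample-size inputs, so 65 cannot be reproduced. Everything else below is assumed, including that the FAP is all treated patients.

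Let N be the CCP size, x its responders, u = 65 − N, and q the response rate outside the CCP. Then

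all-treated ORR = (x + q·u)/65

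CCP ORR − all-treated ORR = (u/65) × (x/N − q).

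Each 10 points of difference between the CCP ORR and q moves the result by 10 × 3/65 = 0.46 points for u = 3, 10 × 6/65 = 0.92 for u = 6, and 10 × 13/65 = 2.00 for u = 13. With a CCP ORR near 20%:

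| u | CCP ORR (exact 95% CI) | CI width, points | All-treated, q = 0 | All-treated, q = 40% | Gap, points |
|---|---|---|---|---|---|
| 3 | 12/62 = 19.4% (10.4 to 31.4) | 21.0 | 12/65 = 18.5% | 13.2/65 = 20.3% | +0.9 to −1.0 |
| 6 | 12/59 = 20.3% (11.0 to 32.8) | 21.8 | 12/65 = 18.5% | 14.4/65 = 22.2% | +1.9 to −1.8 |
| 13 | 10/52 = 19.2% (9.6 to 32.5) | 22.9 | 10/65 = 15.4% | 15.2/65 = 23.4% | +3.8 to −4.2 |

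The fractional numerators are expected values, not patient counts. If q equals the CCP ORR, the gap is zero. Every gap is small beside its interval, and its sign depends on q.

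Larger shifts need stronger assumptions. With 26 of 65 (40%) outside and no responder among them, 8/39 = 20.5% becomes 8/65 = 12.3%, a gap of 8.2 points. Likewise 12/39 = 30.8% becomes 12/65 = 18.5%, a gap of 12.3 points. Nothing in the documents supports a 40% share.

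**The case for a change.** The strongest case for the concern is that its premises are all in the readable text. Efficacy sits in the CCP, baseline and safety sit in the FAP, and dosing on a local result alone is allowed. Submitting tissue is not the same as having a confirming result. The copy-number summary gives neither response nor reasons for exclusion. A supportive figure fixed before database lock also carries more weight than one added once results are known, and it would cost only repeat table runs and one count.

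Those facts stand, and showing the ORR in both sets would be reasonable practice. They do not establish a defect. The case accepts the CCP as the primary set, points to no error and no direction of bias, and allows that the supportive analysis may already be written in the withheld sections. What is left is a preference for extra tables, set against text that cannot be read.

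**Conclusion.** The concern does not hold. Followed as written, the plan gives an ORR in a set that fits its objective, and the visible Screening requirements point to central testing for essentially all patients. Whether a supportive FAP analysis or a count of patients outside the CCP is planned cannot be decided from the public text. Text withheld from publication is not text missing from the plan.

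The size of any difference between the two sets is unknown. With 3 to 13 of 65 patients outside, an ORR near 20% and a response rate outside of 0 to 40%, the gap is at most about 4 points either way, against intervals 21 to 23 points wide.

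This rests on three assumptions: CCP membership means central confirmation, the FAP means all treated patients, and the share outside the CCP is modest. A share near 40% with no responders would give 8 to 12 points, but no passage suggests it.
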